5.7. Screen Failure

A screen failure is a study subject who does not meet all inclusion criteria or fails at least one of exclusion criteria.

6. DATA AND ANALYSIS CONVENTIONS

6.1 General Conventions

The baseline characteristics and demographics of each study subject will be collected during the subject screening process. The subject's medical historical data will be recorded on an electronic case report form (eCRF). The CO measurement data will be downloaded from hemodynamic monitor (Hemosphere advanced monitoring platform). The Roll-in cohort data will be analyzed separately.

[figure not shown]
The data analyses will be conducted with SAS 9.4 software system. Bland Altman analyses will be performed for bias and precision measures. Limits of agreement will be calculated.

6.2 Handling of Missing Data

Missing data are defined as those instances in which data collection was attempted yet failed for some reason (i.e. due to technological, procedural, and/or subject constraints). Demographic and baseline characteristics are collected from the study subjects as part of screening. If missing data are not related to the subject's eligibility criteria, missing data will be presented by the valid sample size in the demographic and baseline characteristics summary statistics table. Subjects with missing data will be included in the final analysis. However, if the missing data are related to the subject's eligibility, this will be considered a protocol deviation, and in this case, the study data from this subject will be reviewed internally, to determine if the subject should be excluded from the final analysis set.

The CO measurements are downloaded from the hemodynamic monitor. Theoretically, there should be no missing data. For data that are missing as defined above, statistical imputation using the SAS imputation method will be utilized.

6.3 Handling of Invalid Data

After downloading the data from the hemodynamic monitors, abnormal observations will be checked and evaluated for hemodynamic stability. Should there be any instability, the result will be rejected. All data will be recorded, and any rejected values will be clearly identified in the eCRF.

The rejection criteria that will be used to determine - hemodynamic instability are detailed below:

- Mean arterial pressure (MAP): If MAP varies > 15% during the 30-sec period of each intermittent thermodilution, the bolus will be rejected.
- Pulse rate: If Pulse varies > 15% during the 30-sec period of each ITD, the bolus will be rejected.
- PhysioCal: If PhysioCal is not at least 30 beats, the bolus will be rejected.

•

Upon taking four (4) thermodilution measurements and given the above criteria for classifying data as invalid, Edwards proposes to remove the one measurement that is the greatest outlier of the four. If upon the rare occasion two or more outliers measure greater than 15% from the mean, within a series of measurements, or hemodynamic instability results when these observations are taken, the clinician will repeat the series. If this scenario of repeating the series is missed by the clinican during the clinical procedure and discovered by the statisticians during data review, the outliers will be analyzed separately. In addition to the results for the collected parameters, the number of subjects with less than 3 and number of subjects with at least 3 valid values, and results of subjects will be tabulated separately, and reported. Those subjects who have less than 3 valid measurements and were missed for repeated testing by the clinician performing the thermodilutions will be considered as protocol deviations or protocol violations.

Additionally, a supplementary exploratory analysis will be reported using all the recorded values (valid and invalid) to assess the impact of the excluded values.

[figure not shown]
7. SUMMARY OF BASELINE INFORMATION

7.1 Subject Eligibility Criteria

Inclusion Criteria

- 1. Subjects who are 12 to 18 years of age
- 2. Subjects who have signed the Informed Consent Form
- 3. Subjects who are projected to receive Swan-Ganz catheter as part of procedure/standard of care with intermittent cardiac output measures
- 4. For those Subjects who have had a cardiac transplant, Subjects must be at least two weeks post cardiac transplantation Subjects
- 5. Subjects with planned pressure monitoring with an arterial line

Exclusion Criteria

- 1. Subjects with contraindications for Pulmonary Artery Catheters Placement and monitoring (recurrent sepsis, or with hypercoagulopathy);
- 2. Subjects with contraindications for Arterial Line Placement;
- 3. Subjects with an extreme contraction of the smooth muscle in the arteries and arterioles in the lower arm and hand (i.e., Raynaud's Disease).
- 4. Subjects with a physical site area too limited for proper Sensor placement
- 5. Subjects with finger size less than the smallest finger cuff size
- 6. Documented ≥ moderate pulmonary hypertension (PAPm > 25 mmHg, PVRI > 3.0 WUxm2)
- 7. Presence of intracardiac shunting (i.e., ASD, VSD)
- 8. Aorto-pulmonary collaterals
- 9. ≥ Moderate tricuspid regurgitation, per echocardiogram criteria
- 10. > Moderate Aortic or pulmonary regurgitation, per echocardiogram criteria
- 11. Persistent cardiac arrythmias during the cardiac catheterization period (> 3min)
- 12. Vascular abnormalities of the arterial system (i.e., connective tissue disorders, mid-aortic syndrome)"

7.2 Demographics and Baseline Characteristics

The baseline characteristics and demographics of each study subject will be collected during the subject screening process.

7.3 Medical History

The subject's medical historical data will be recorded on an electronic case report form (eCRF). The CO measurement data will be downloaded from hemodynamic monitor (Hemosphere advanced monitoring platform).

7.4 Risk Assessments

Any events associated with a commercially available study device will be reported in accordance with the Medical Device Reporting (Complaints) regulation (21 CFR Part 803), while events associated with the investigational device will be reported under the IDE program (812.150).

Below is a list of anticipated risks that may be associated with the use of Swan-thermodilution pulmonary artery catheter.

- Perforation of the pulmonary artery
- Pulmonary infarction
- Cardiac arrhythmias
- Knotting
- Sepsis/Infection
- Right bundle branch block
- Complete heart block

	Revision Date: De	ecember 2, 2020	Rev	В	For Use Only by Affiliates of Edwards Lifesciences	Page 19
Edwards	Title	Statistical Analysis Pl Nonrandomized, Obso Monitoring in Pediatri	ervatio	onal St		

- Tricuspid and pulmonic valve damage
- Thrombocytopenia
- Pneumothorax
- Thrombophlebitis
- Nitroglycerin absorption
- Thrombosis
- Allergic reaction to latex

FloTrac sensor

[figure not shown]
The vascular access obtained is standard clinical care and the addition of the FloTrac arterial transducer is standard procedure and does not impose any additional risk to the patient. There is no measurable increased infectious risk with the temporary use of the FloTtrac sensor.

Below is a list of anticipated risks that may be associated with the use of the ClearSight finger cuff.

- Discomfort where the cuff is applied
- Discoloration of digit distal to the cuff
- Pain associated with inflation of the cuff
- Slight numbness of the fingertip

Below is a list of anticipated risks that may be associated with the use of ForeSight Elite Sensors.

- Allergic reaction to sensors
- Skin irritation

[figure not shown]

7.5 Study Procedure

The schedule of events is illustrated in the following table.

Study Procedure / Exam	Subject Screening	Procedure	30-Day Follow Up (±14 Days)
Obtain Informed Consent	Χ		
Perform Inclusion / Exclusion Evaluation	Х		
Obtain Medical History / Subject Demographics ¹	Х		
Assign Subject ID		X	
Enter Subject Data into Monitor		X	
Vital Signs		X	
Monitoring Duration		X	
Data download from Monitor		X	
Obtain Fluid and Vasoactive		V	
Medication Administration Record ²		X	
Record Adverse Events, if applicable		X	Х
Phone Contact 30-day follow up / Mortality Determination			Х

¹ Medical History / Subject Demographics / Surgical and Clinician Demographics can be obtained prior to procedure, either at the screening visit or on the day of procedure.

8. STATISTICAL ANALYSIS OF STUDY ENDPOINTS

8.1 Primary Endpoint

The primary objective of this study is to demonstrate that monitoring of cardiac output with Sawn-Ganz, FloTrac, and ClearSight is comparable as determined by the Bland-Altman method of bias. To demonstrate this comparability, the bias calculation will be assessed separately.

Summary statistics and statistical comparison

The CO measurements from both investigational and reference device systems will be summarized using descriptive statistics including mean, median, minimum, maximum, standard deviation, Q1 (first quantile), and Q3 (third quantile). Additionally, p values from paired t-test will be provided to test the difference.

8.1.2 Primary endpoint analysis with Bias calculated by CO

The primary endpoint of the bias between the matched pairs of CO measurements as determined by the Bland-Altman method will be tested as below using the one sample t-test.

The hypothesis for bias is:

H0: bias <-0.5 or bias >0.5

H1: -0.5≤ bias ≤0.5

See section 3.1 for details.

8.1.3 Limits of Agreement

Limits of agreement will be computed using Bland-Altman methods. Components of the one-way analysis of variance will be used to estimate variance of multiple between-device differences for the same subject. These components of variance measures include the mean square for subjects (SS), and residual mean square (RMS). The differences between the average difference across subjects will be estimated from the difference between SS and RMS. This difference will be divided by $M=((\sum m_i)^2 - \sum m_i^2)/(n-1)^*(\sum m_i)$, where n=1 total number of subjects, and m_i is the number of pairwise difference measurements for the *ith* subject. The estimated component of variance, which represents the heterogeneity, is estimated as (SS – RMS)/M. The total variance (TV) for single differences on different subjects is estimated by the sum of these two components: TV = (SS – RMS)/M + RMS. The resulting lower and upper limits of agreement will be estimated with 97.5% confidence mean(diff) \pm 1.984*TV for a two-sided test.

Revision Date: December 2, 2020

Rev

For Use Only by Affiliates of Edwards Lifesciences

Page 22

Title

Statistical Analysis Plan for A Prospective, Single-Arm, Nonrandomized, Observational Study of Cardiac Output Monitoring in Pediatric Patients

В

We want agreement to be the same or at least similar over the range of CO and CI measurements. Plots of the difference bias between device pairings (ClearSight vs Swan-Ganz, and FloTrac vs Swan-Ganz), for CO and CI measurements, on average of the two device measurements will be performed, with reference lines including zero, mean difference, and lower and upper limits of agreement. Two-sided 97.5% LOA will be calculated for bias between device pairings⁹. The statisticians will determine whether the standard deviation of the mean difference is constant or non-constant for each measure. The mean difference and standard deviation about the mean difference will be estimated for all measurements. The difference measures will be tested for heterogeneity using components of variance methods. The variance for single differences between device pairs of measurements, on different subject, will be plotted. Also, mean difference will be plotted on the order in which observations are recorded for each subject.

Visual check of the bias spread pattern and deviation using scatter plots of bias and/or percent error versus Fick principle reference mean CO, and scatter plot of bias and the percent error versus target device mean CO, with reference lines zero and limits of agreement ($\delta \Theta \delta \delta$) to the plot will be performed.

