The sample size calculation for this hypothesis is based on the one-sample t-test for equivalence. The desired outcome is to reject the null hypothesis at the 0.025 significance level. For this equivalence test of bias, two comparisons will be performed: FloTrac vs Swan-Ganz and ClearSight vs Swan-Ganz. In order to preserve the overall type 1 error rate at 0.05, the Bonferroni Correction will be used to adjust for multiple comparisons. Assuming a true mean bias of 0.0 and a SD of 1.0 l/min in the cardiac output, the sample size required for δ =0.5, alpha=0.025, and power=90% to reject the null hypothesis is 45, ignoring the ICC. After considering ICC for eight repeated measures (m=8), adjusting for multiple comparisons, considering comparisons of between two target devices and a reference device pairs, simultaneously, a sample size of 60 Subjects is needed. After considering a 34.5% rejection rate for hemodynamic instability, 10% lost to follow-up rate, and 6 roll-in Subjects for the learning curve, up to 108 (102) evaluable Pivotal Subjects and 6 Roll-in Subjects) will be enrolled into the study.

By simulating the study results with a mixed effect model, using repeated measurement data collected from a similar study, although the sample size estimate from this approach is conservative, it is reasonable and rational.

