3.1 Primary effectiveness endpoint

By the CO measurement from Swan-Ganz, FloTrac, and ClearSight, and Fick principle, the variable bias (X) is derived for statistical analysis:

$$x_{ij} = CO_{tij} - CO_{rij}$$

Where x_{ij} is the bias of ith subject and jth matched pair repeated measurements, CO_{tij} is CO measurement of the ith subject at jth repeated measurement of test device, such as Swan-Ganz, FloTrac, and ClearSight, CO_{di} is the CO measurement of ith subject at jth repeated measurement of reference device the Swan-Ganz thermodilution pulmonary catheter. Here $i=1,\ldots,n$ (the estimated sample size, 102), $j=1,\ldots,m$ (the planned repeated measurements, 8).

3.1.2 97.5% Confidence Intervals for bias using bootstrap and limit of agreement methods

Bootstrap method will be used to estimate two-sided 97.5% confidence intervals for all CO and CI bias measures under study. This will be performed for all analysis datasets as well as those data with rejected data. Results will be compared.

Revision Date: December 2, 2020

Rev

For Use Only by Affiliates of Edwards Lifesciences

Page 13

Title

Statistical Analysis Plan for A Prospective, Single-Arm, Nonrandomized, Observational Study of Cardiac Output Monitoring in Pediatric Patients

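### The limits-of-agreement divisor M lacks denominator brackets; computed as printed it removes the between-subject variance, which affects the reported limits and plot lines only

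*Combined protocol and SAP*

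**What the plan says.** SAP 8.1.3 builds the limits from a one-way analysis of variance of the between-device differences. SS is defined as the subject mean square and RMS as the residual mean square. The SAP takes SS − RMS and continues: "This difference will be divided by" M, printed as `M = ((Σm_i)² − Σm_i²)/(n−1)*(Σm_i)`. Here n is the number of subjects and m_i the number of paired differences for subject i. The printed parentheses balance, there is an explicit asterisk, and no bracket encloses the product (n−1)*(Σm_i).

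The section goes on: "The estimated component of variance, which represents the heterogeneity, is estimated as (SS – RMS)/M". Total variance is TV = (SS − RMS)/M + RMS, and the limits are the mean difference plus or minus "1.984*TV for a two-sided test". Their level is given as 97.5%, and the section later repeats: "Two-sided 97.5% LOA will be calculated for bias between device pairings".

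No other part of the protocol or SAP gives a bracketed M or a worked value for M, TV or the limits. SAP 8.1.3 cites a published method for agreement with multiple observations per individual (SAP reference 9) but does not set out that method's formula.

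**The concern.** In a one-way analysis of variance with m pairs per subject, the expected subject mean square is the residual variance plus m times the between-subject variance. Dividing SS − RMS by M therefore recovers the between-subject variance only if M equals m in the balanced case. That requires both (n−1) and Σm_i in the denominator. The printed line divides by (n−1) and then multiplies by Σm_i.

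SAP 2.3.1 describes between-subject variation as the dominant part. If the formula is coded as it stands, that part disappears and only within-subject scatter is left in the limits. The error runs in one direction: the limits come out too narrow, and each device looks more interchangeable with thermodilution than it is. The study is meant to support wider paediatric indications, and limits of agreement are a planned output (SAP 6.1, 8.1.3).

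**Working it through.** **Inputs**

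- n = 102 (SAP 3.1: "the estimated sample size, 102").
- m = 8 for every subject (SAP 3.1: "the planned repeated measurements, 8").
- Total variance 1.0, from SAP 2.3.1: "Assuming a true mean bias of 0.0 and a SD of 1.0 l/min in the cardiac output".
- ICC 0.94 to 0.98 (SAP 2.3.1, from literature in children).

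**The plan's own figures.** The SAP gives no value for M, TV or the limits, so there is nothing to reproduce directly. Its use of the ICC can be checked: √(0.98 + 0.02/8) = 0.991211, which matches SAP 2.3.1.

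**Step 1: M.**

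- Σm = 102 × 8 = 816, and Σm² = 102 × 64 = 6,528.
- (Σm)² − Σm² = 665,856 − 6,528 = 659,328.
- Bracketed: 659,328/(101 × 816) = 8, equal to m as it must be.
- As printed: 659,328/101 = 6,528, and 6,528 × 816 = 5,326,848.
- Ratio: 5,326,848/8 = 665,856 = 816². The printed M is always too large by (Σm)².

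The result does not hinge on these counts. With n = 60 and m = 8, M is 1,843,200 instead of 8. With n = 102 and m = 2 (if each averaged set of four counts as one pair), it is 83,232 instead of 2.

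**Step 2: total variance.** RMS = 1 − ICC, and SS = RMS + 8 × ICC in expectation.

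| ICC | SS | RMS | Between-subject, bracketed | Between-subject, as printed | TV, bracketed | TV, as printed |
|---|---|---|---|---|---|---|
| 0.98 | 7.86 | 0.02 | 7.84/8 = 0.98 | 7.84/5,326,848 ≈ 0.0000015 | 1.00 | 0.0200 |
| 0.94 | 7.58 | 0.06 | 7.52/8 = 0.94 | 7.52/5,326,848 ≈ 0.0000014 | 1.00 | 0.0600 |

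A simulation (2,000 runs, n = 102, m = 8, ICC 0.98) gave a mean TV of 0.0200 as printed and 0.998 bracketed.

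**Step 3: half-width of the limits, in L/min.** With M bracketed and TV = 1.00 it is 1.984, whether TV or its square root is used.

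| ICC | 1.984 × √TV, M as printed | Too narrow by | 1.984 × TV, M as printed | Too narrow by |
|---|---|---|---|---|
| 0.98 | 0.281 | 7.1 times | 0.040 | 50 times |
| 0.94 | 0.486 | 4.1 times | 0.119 | 17 times |

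For normal differences with variance 1.0, such limits would contain about 22% to 37% of single differences (square-root form) or 3% to 9% (printed form).

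**Step 4: the rest of the sentence.** TV is a variance, in (L/min)², so the limits need √TV; the two coincide only when TV = 1. The 0.975 t quantile at 100 degrees of freedom is 1.984, so the printed multiplier gives two-sided 95% limits. A two-sided 97.5% multiplier is the 0.9875 quantile, about 2.275 at 101 degrees of freedom. Bracketing M cures neither problem.

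**The case against.** The best reply is that this is notation, not method. The section names Bland-Altman limits, a one-way analysis of variance and a published repeated-measures source, so the intended M is recognisable. A statistician following that source would probably supply the brackets, and a divisor in the millions with eight pairs per subject should be noticed. The line also shows damage from text extraction (the asterisk appears as a superscript), so a denominator grouping lost from a built-up fraction cannot be fully excluded. Against this, the parentheses balance, so loss of a single bracket does not explain it, and the printed asterisk suggests an inline original. SAP section 1 presents the document as detailed instructions and requires deviations from it to be documented. The formula should therefore be right as written.

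A second reply is that the size rests on an uncertain ICC. That stands. SAP 2.3.1 does not say that 0.94 to 0.98 was estimated from between-device differences, although it applies the figure to the variance used for the bias sample size. At an assumed ICC of 0.5 the limits would be 1.4 times too narrow in the square-root form and 2 times in the printed form. The between-subject term is lost at any ICC.

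A third reply is that no decision depends on the limits. That also stands. A reader might infer that the error flatters the primary or secondary endpoint, and the documents do not support this. The primary endpoint is a one-sample t-test of bias against ±0.5 L/min (SAP 8.1.2). Percent error is computed from each pair's absolute difference over the reference value and tested against 30% (SAP 3.2.1, 8.2.1). SAP 2.3.2 does quote a paper that derives percent error from limits of agreement, but the SAP's operative formula does not do so. The heading of SAP 3.1.2 mentions limit-of-agreement methods, but its text describes only bootstrap intervals. The SAP sets no acceptance criterion for the limits.

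**Conclusion.** The formula for M is wrong as printed. It exceeds the correct divisor by a factor of (Σm_i)² and sets the between-subject variance component to practically zero, whatever the number of subjects or pairs. This part needs no assumption beyond normal operator order.

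The effect on the limits (4 to 7 times too narrow on the SD scale, about 17 to 50 times if 1.984*TV is also followed literally) assumes a total variance of 1.0 and an ICC of 0.94 to 0.98 for the between-device differences. The damage is confined to the reported limits of agreement and the reference lines on the agreement plots. A reader might also conclude that the trial's limits will certainly be misreported; the documents do not show that, because a programmer working from the cited method could correct the line unprompted. It should be corrected in the SAP all the same, together with the two other faults in the limits sentence.

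**What to change.** In SAP 8.1.3:

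1. Write M = [(Σm_i)² − Σm_i²] / [(n−1) × Σm_i].
2. Add a programming check that M = m when all subjects have m pairs.
3. Write the limits as the mean difference ± multiplier × √TV. Test the code on data whose TV is not 1, since the square root makes no difference at 1.
4. Make the multiplier and the stated level agree: either label limits based on 1.984 as two-sided 95%, or keep 97.5% and use the matching t quantile (about 2.275 at 101 degrees of freedom).

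The definitions of SS and RMS as mean squares are already in the section and need no change. The cost is one formula and one sentence in the SAP, with no effect on design, data collection, sample size or the endpoint tests.

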2.3.3 Sample size consideration for bias calculated with cardiac index

The bias between the matched pairs of CI measurements, as determined by the Bland-Altman method, must be smaller than the minimum clinical difference δ , which is the value that is large enough to claim difference.

[figure not shown]
The hypothesis for bias is:

H0: bias $<-\delta$ or bias $>\delta$

H1: $-\delta$ ≤ bias ≤ δ

Because there are no valid publications found through internet searching to design the settings in sample size estimation based on CI, the relation between CI and CO is used in sample size estimation here. Cardiac index (CI) is defined as cardiac output (CO)/body surface area (BSA). By the results from Cattermole G. N., Leung P. Y. M., Mak P. S. K. et al. 2010 and Cattermole G. N., Leung P. Y. M., Ho G. Y. L. et al. 2017, the BSA value for kid with age \geq 8 is greater than 1, target on Chinese population in Hong Kong. For the age group from 12 to 18 years, it is around 1.5. If the study subjects are from developed country the BSA value possibly will be larger. If the study targets at developing country population, this value possibly will be smaller. By this consideration BSA=1.2 is used in bias adjustment and the SD adjustment. The SD used in sample size estimation for CI will be 0.85 ($SD_{CI} \approx \frac{SD_{CO}}{BSA} \approx 0.85$).

In this study eight repeated measurements or sub sample sections for each study subject will be taken during the cardiac catherization case, thus intra-cluster correlation ecoefficiency ICC is a factor to be considered in sample size estimation. Here $ICC = \frac{\delta_s^2}{\delta_s^2 + \delta_{ss}^2}$. δ_s^2 is the variance component of study subject. δ_{ss}^2 is the variance component of sum sample. By literature the ICC in children ranges from 0.94 to 0.98. The variation of study subject is dominant. Fixed the study subjects, the more sub-samples taken the less δ_{ss}^2 will be by a factor 1/m. This will reduce the total variance applied in sample size calculation. Using ICC=0.98, and SD=1 (Variance=1) as an example, as an example, for m=8, the adjusted variance will be $0.98 * 0.7225 + (1-0.98) * \frac{0.7225}{8} = 0.70985$ and the SD=0.8425.

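### SAP 8.1.3 multiplies a variance, not a standard deviation, to get the limits of agreement, and calls them two-sided 97.5% although 1.984 is the two-sided 95% multiplier

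*Combined protocol and SAP*

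**What the plan says.** SAP 8.1.3 takes the one-way analysis of variance of the repeated between-device differences and forms a between-subject component, (SS – RMS)/M, from the subject mean square SS, the residual mean square RMS and a divisor M that reflects the number of differences per subject. It adds RMS to this: "The total variance (TV) for single differences on different subjects is estimated by the sum of these two components". The limits then follow directly: "The resulting lower and upper limits of agreement will be estimated with 97.5% confidence", as the mean difference ± "1.984*TV for a two-sided test". No square root appears.

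The next paragraph repeats the level: "Two-sided 97.5% LOA will be calculated for bias between device pairings". It also asks for plots of difference against average, for CO and CI and for both device pairs, "with reference lines including zero, mean difference, and lower and upper limits of agreement".

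The SAP's planning values for the spread of the differences are in section 2.3.1 for CO ("Assuming a true mean bias of 0.0 and a SD of 1.0 l/min in the cardiac output") and section 2.3.3 for CI ("The SD used in sample size estimation for CI will be 0.85").

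**The concern.** TV is a sum of mean-square terms, so for cardiac output it is in (L/min)². Adding a multiple of it to a mean difference in L/min mixes units, and the resulting limits have the wrong width whenever the SD differs from 1.

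Separately, the multiplier and the stated level do not belong together. The 97.5% label looks deliberate: it matches the Bonferroni significance level of 0.025 in SAP 2.3.1 and the two-sided 97.5% intervals for bias in SAP 3.1.2.

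The limits of agreement are what tells a reader how far a single FloTrac or ClearSight value may lie from thermodilution. Followed as written, the SAP would report them at the wrong width and under the wrong level, in a direction that depends on the SD observed.

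**Working it through.** **Inputs.** n = 102 and m = 8 differences per subject (SAP 3.1), so n – 1 = 101 df. Planning SD 1.0 for CO (SAP 2.3.1) and 0.85 for CI (SAP 2.3.3). SDs of 0.5 and 1.5 are my assumptions, added only to show the direction of the error on each side of 1.

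**Step 1: where 1.984 comes from.** t(0.975, 101) = 1.9837, which rounds to 1.984. The same rounding holds for 98 to 101 df. So the figure is reproduced as the two-sided 95% multiplier at the planned n.

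**Step 2: what two-sided 97.5% requires.** With 1.25% in each tail, t(0.9875, 101) = 2.2753. The normal value, the smallest possible for any df, is 2.2414. No choice of df makes 1.984 a two-sided 97.5% multiplier. The shortfall is 1 – 1.984/2.2753 = 1 – 0.872 = 12.8%.

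**Step 3: effect of the missing root.** With TV = SD²:

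- as written: 1.984 × SD²
- 95% limits: 1.984 × SD
- 97.5% limits: 2.2753 × SD

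| SD of differences | As written | 95% | 97.5% | Written / 95% | Written / 97.5% |
|---|---|---|---|---|---|
| 0.5 (assumed) | ±0.496 | ±0.992 | ±1.138 | 0.50 | 0.44 |
| 0.85 (CI planning) | ±1.433 | ±1.686 | ±1.934 | 0.85 | 0.74 |
| 1.0 (CO planning) | ±1.984 | ±1.984 | ±2.275 | 1.00 | 0.87 |
| 1.5 (assumed) | ±4.464 | ±2.976 | ±3.413 | 1.50 | 1.31 |

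The written half-width equals the 97.5% half-width when 1.984 × SD² = 2.2753 × SD, that is at SD = 2.2753/1.984 = 1.147. Below that the written limits are too narrow for their label; above it they are too wide. Against 95% limits the crossing point is SD = 1.

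**Step 4: the divisor M.** As printed, M is the numerator over (n – 1), followed by a multiplication by Σm. The intended divisor is the product (n – 1) × Σm. For n = 102 and m = 8, Σm = 816 and M = (816² – 102 × 64)/(101 × 816) = 659,328/82,416 = 8.0, as it should be with equal cluster sizes. Evaluated left to right, the printed form gives 659,328/101 × 816 = 5,326,848, which would all but remove the between-subject component.

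**The case against.** The strongest point is that the root sign may simply have been lost when the PDF was read. The text around this formula is visibly damaged, the section says it follows Bland-Altman methods and cites their paper on repeated observations, and a programmer who knows the method would take the root. Roots did survive in the SD formula of SAP 2.3.1, but that is a displayed equation and this is inline text. So the missing root needs checking against the source file. The multiplier mismatch does not depend on this, because the number and the label are both plain text.

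Second, if the label is the slip and 95% limits were meant, 1.984 is right for the planned n, and the 13% shortfall disappears. That is fair, and the percentages measured against 97.5% depend on the label governing. The SAP's consistent use of 0.025 and 97.5% elsewhere favours the label, but either way number and label cannot both stand.

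Third, the consequence is limited. The primary endpoint in SAP 8.1.2 "will be tested as below using the one sample t-test", and the percent error in SAP 3.2.1 and 8.2.1 is computed from individual paired values. Neither uses the limits, and no acceptance criterion is set on them. At the CO planning SD the missing root changes nothing, and CI is exploratory. All of this stands and bounds the point.

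Fourth, some details depend on what is finally analysed. With 60 subjects the multipliers are about 2.00 and 2.30. SAP 2.2.1 averages three of four readings, so m may not be 8. TV combines two mean squares, so n – 1 df is an approximation, a close one when between-subject variance dominates as SAP 2.3.1 assumes. None of these removes either error.

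**Conclusion.** The point holds. As written, SAP 8.1.3 scales the limits of agreement by a variance and pairs a 95% multiplier with a 97.5% label; nothing elsewhere in the protocol or SAP corrects either.

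Taking the label and n = 102 at face value, the half-width is 13% too narrow for CO at the planning SD of 1.0, entirely from the multiplier, and 26% too narrow for CI at 0.85, from both errors together. If 95% limits were meant, CO is unaffected at SD 1.0 and CI is 15% too narrow. If the root was only lost in reading the PDF, the 13% multiplier shortfall against the label remains at every SD.

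The error reaches the reported limits and the CO and CI difference plots. It does not touch the primary or secondary tests or the sample size. It should be corrected before analysis, but it does not threaten the study's main conclusion.

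**What to change.** In SAP 8.1.3, write the limits as mean difference ± k × √TV, state one level in both paragraphs, and use the matching k on the actual n – 1 df: t(0.9875, n – 1) to keep two-sided 97.5%, or t(0.975, n – 1) if the limits are relabelled 95%. Compute k from the number of subjects analysed instead of fixing it at 1.984.

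In the same line, bracket the divisor as M = ((Σm)² – Σm²)/((n – 1) × Σm), so that it cannot be programmed in the wrong order.

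The cost is one line in the SAP and one in the program before analysis. Sample size, data collection and the endpoint tests are unchanged.
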